3.1 Inclusion Criteria

- Patients aged $>18y$
- Histologically confirmed diagnosis of UC of upper and/or lower urinary tract
- Histologically or radiologically confirmed metastatic disease
- Treatment with pembrolizumab in patients progressed after previous platinum-based chemotherapy
- Treatment with pembrolizumab as a first-line therapy in the platinum-unfit patients
- Treatment with enfortumab vedotin in patients progressed to previous platinum-based chemotherapy and anti-PD-1/PD-L1 inhibitor.

3.2 Exclusion Criteria

- Patients without histologically confirmed diagnosis of UC
- Patients without histologically or radiologically confirmed metastatic disease

3.3 Estimated Enrollment

In order to determine the minimum sample size for the purpose of the analysis on patients treated by pembrolizumab, we identified the smallest subpopulation among the planned sub-analyses, which was represented by obese patients with advanced UC. According to the literature, the incidence of obesity can be estimated at 30% in patients with UC [21]. In the study that led to the FDA approval of Pembrolizumab in UC patients [15], the median OS in the standard control arm with chemotherapy was 7.4 months, with a hazard ratio of 0.73. In our study, we set a significance level of 0.05 and the power to 80% for a minimal observation time of 12 months [22,25]. Under these conditions, we estimated an enrollment of 110 obese UC patients, in order to expect to observe at least 78 events in this group, which corresponds to an estimated overall study population of 367 patients affected by advanced UC.

In the study that led to the FDA approval of enfortumab vedotin in UC patients [17], the estimated percentage of patients alive at 12 months was 51.5% (95% CI, 44.6 to 58.0) in the enfortumab vedotin group and 39.2% (95% CI, 32.6 to 45.6) in the chemotherapy group with a delta of 12.3 among the two groups. In this study,

The ARON PROJECT

Global experiences, perspectives and access to cure in patients with genitourinary tumors

we tested the hypothesis that, using the enfortumab vedotin in clinical practice, OS would reach at least 60% after 12 months from the start of therapy. Study plan will include at least 361 patients with an estimated drop out of 10–15%. It was calculated that a minimum of 311 evaluable patients should be enrolled with an α of 0.05 and a β of 0.80 (STATASOFT).

4. Statistical Analysis and Data Collection

PFS and OS will be estimated by Kaplan-Meier method with Rothman's 95% confidence intervals (CI) and compared by using the log-rank test. Univariate and multivariate analyses will be performed by using Cox proportional hazards models. The chi-square test will be used to compare categorical end-points. Significance levels will be set at a 0.05 value and all p values will be two-sided. The statistical analysis will be performed using MedCalc version 19.6.4 (MedCalc Software, [name]).

Clinical data retrospectively extracted from paper and electronic charts will be collected in Excel datasets. The data will be anonymized and a code will be used for each individual patient included in the study. For each patient, the following data will be collected in the database of each participating institution: histology, surgery, sites of metastases, Body Mass Index (BMI), concomitant medication, radiotherapy, laboratory tests and treatments. Patients without sufficient data on follow-up and response to therapy will be excluded from this study.

5. End-dates for Data Collection and Publication

Due to the large number of Centers involved from different Countries, we have scheduled a series of deadlines in order to complete step-by-step the planned analyses and prepare the manuscripts for publication:

- The first deadline is July 1st, 2024 - analysis of data collection and preparation of four of our planned manuscripts within 31th August, 2024
- The second deadline is September 1st, 2024 - analysis of data collection and preparation of the other planned manuscripts within October 31th, 2024

For each manuscript, one author's name for each Institution involved in this project will be considered. We will consider, according to Journal policies, two names for each Oncological Center that has enrolled at least 50 patients in the dataset or which has substantially participated to the different phases of the manuscripts.

Before the submission, a draft of each manuscript will be sent to all the authors from the Institutions involved in order to revise potential errors and propose additional comments and suggestions.

Potential publication fees will be sustained by the Center of the Principal Investigator (Macerata Hospital).

6. Data Confidentiality and Management

Information about study subjects will be kept confidential and managed under the

The ARON PROJECT

Global experiences, perspectives and access to cure in patients with genitourinary tumors

applicable laws and regulations. The data collection system for this study uses built-in security features to encrypt all data for transmission in both directions, preventing unauthorized access to confidential participant information. Access to the system will be controlled by a sequence of individually assigned user identification codes and passwords, made available only to authorized personnel who have completed prerequisite training. The investigator must ensure anonymity of the patients; patients must not be identified by names in any documents.

The Principal Investigator is responsible for assuring that the data entered are complete and accurate. Essential documents (written and electronic) should be retained for a period of seven (7) years from the completion of the Study.

7. Ethical Consideration

The ARON-2 Study will be conducted according to Good Clinical Practice (GCP) and has been designed with the ethical principles laid down in the Declaration of Helsinki on human experimentation. The Study will be approved by the Ethical Committees of the participating Institutions according to local guidelines.

8. Informed consent procedures

Eligible patients may only be included in the study after providing written (witnessed, where required by law or regulation), informed consent form. Informed consent must be obtained before conducting any study-specific procedures (i.e.,

any of the procedures described in the protocol). The process of obtaining informed consent should be documented in the patient source documents.

9. Fundings and Fees

No fees are required from or provided to the Centers that participate to the ARON-2 project. Potential publication fees will be sustained by the PI of the Study.

10. References

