2.2 Secondary End-Points

- To apply artificial intelligence technology to the study of real-world data for clustering and Artificial Neural Network analyses

The ARON PROJECT

Global experiences, perspectives and access to cure in patients with genitourinary tumors

- To assess the prognostic role of smoking attitude, obesity, age, renal insufficiency, primary tumor location, histology and concomitant medication in patients treated with pembrolizumab and/or enfortumab vedotin
- To compare different therapeutic sequences in mUC patients

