2.3 Evaluation of the Endpoints

- Overall Survival (OS) will be defined as a time from the start of the therapy until death from any cause
- Progression-Free Survival (PFS) will be defined as a time from the start of the therapy until progression or death from any cause. Patients switched to the following line of treatment without progression or lost at follow-up at the time of analysis were censored at their last follow-up date
- Radiological assessment was performed according to the RECIST 1.1 criteria [23] and the data on objective response (complete regression=CR, partial regression=PR, stable disease=SD or progressive disease=PD) will be collected and analyzed
- The Overall Response Rate (ORR) and Disease Control Rate (DCR) will be defined as the rates of CR + PR and CR + PR + SD, respectively (according to the RECIST 1.1 criteria) [23]
- Treatment related adverse events (e.g., cutaneous toxicity, neurological toxicity and hyperglycemia/mellitus diabetes) will be assessed according to

The ARON PROJECT

Global experiences, perspectives and access to cure in patients with genitourinary tumors

the Common Terminology Criteria for Adverse Events (CTCAE) v 5.0 [24].

Grade ≥ 3 adverse events will be analyzed with a special focus

3. Study Population

The ARON-2 study retrospectively analyze patients treated with pembrolizumab, as first-line therapy in platinum-unfit patients or as second-line therapy in patients progressed after previous platinum-based chemotherapy, and/or enfortumab vedotin, as third-line therapy in patients previously treated with platinum-based chemotherapy and subsequently with PD-1 or PD-L1 inhibitor.

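### The 80% power behind 78 events, 110 obese and 367 pembrolizumab patients fits a comparison with a published chemotherapy median, not the obese versus non-obese comparison that the protocol plans

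*Protocol*

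**What the plan says.** Section 3.3 of the protocol sets the pembrolizumab sample size on one subgroup: "we identified the smallest subpopulation among the planned sub-analyses, which was represented by obese patients with advanced UC". The obese share comes from the literature: "the incidence of obesity can be estimated at 30% in patients with UC". The effect size comes from the pembrolizumab registration trial, where "the median OS in the standard control arm with chemotherapy was 7.4 months, with a hazard ratio of 0.73". The error rates follow: "we set a significance level of 0.05 and the power to 80% for a minimal observation time of 12 months". Two references on exponential life testing are cited for the method. The result is 78 events among 110 obese patients, scaled up to 367 patients overall.

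The obesity objective is in section 2.2: "To assess the prognostic role of smoking attitude, obesity, age, renal insufficiency, primary tumor location, histology and concomitant medication". Section 4 says that PFS and OS will be estimated by Kaplan-Meier and "compared by using the log-rank test", with Cox models for univariate and multivariate analysis. It adds: "Significance levels will be set at a 0.05 value and all p values will be two-sided". It lists no test against a fixed median, and no chemotherapy arm is collected.

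Section 3 describes the pembrolizumab patients as treated "as first-line therapy in platinum-unfit patients or as second-line therapy in patients progressed after previous platinum-based chemotherapy". The reference list gives the trial behind the 7.4 months and HR 0.73 as a trial of second-line therapy.

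**The concern.** The only hazard ratio in the calculation is a treatment effect, pembrolizumab against chemotherapy. The planned question is whether obesity is prognostic among patients who all received the drug. The first can be sized on events in the obese group alone, because the reference is a fixed published number. The second compares two observed groups of unequal size and needs several times as many deaths for the same hazard ratio. Section 3.3 presents 367 as the minimum for the planned sub-analyses, so a reader will take the 80% as power for those sub-analyses.

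At stake is how a non-significant obesity result is interpreted. If the true hazard ratio were 0.73, the chance of missing it would be about 36% to 46%, not the 20% that the stated power suggests.

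**Working it through.** **Inputs from the protocol.** Reference median 7.4 months and HR 0.73; alpha 0.05 and power 80%; 110 obese patients, 78 events, 30% obese, 367 in total (all section 3.3); two-sided testing (Section 4).

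**Input that is an assumption.** HR 0.73 for obese versus non-obese. The protocol gives no obesity effect, so its one hazard ratio is borrowed for illustration.

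**1. Reproducing the plan's figure.** One group against a fixed exponential reference, two-sided:

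d = (1.960 + 0.842)² / (ln 0.73)² = 7.849 / 0.0990 = 79.2 events.

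The exact chi-square version gives 77. The stated 78 lies between them; power at 78 events is 79.4% (normal) or 80.8% (exact). Alternatives do not fit: the one-sided version gives 61 to 65 events, and a two-group 1:1 comparison gives 317 (Schoenfeld) or 323 (Freedman). The total follows from 110 / 0.30 = 366.7, so 367.

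**2. Deaths needed for obese versus non-obese.** Schoenfeld's formula at 30:70:

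D = 7.849 / (0.30 × 0.70 × 0.0990) = 377.4, so 378 deaths.

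**3. Power with 367 patients.** Power = Φ(√(0.21 × D) × 0.3147 − 1.960):

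| Deaths D | Share dead | Basis | Power |
|---|---|---|---|
| 206 | 56% | 12 months, median 7.4 / 0.73 = 10.1 months | 54% |
| 248 | 67.5% | 12 months, median 7.4 months | 62% |
| 260 | 71% | the plan's own 78 / 110 | 64% |
| 367 | 100% | all patients die | 79% |

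The 12-month shares are 1 − exp(−ln 2 × 12 / median), which gives 0.560 and 0.675.

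**4. Detectable hazard ratio at 80% power.** exp(−2.802 / √(0.21 × D)) gives 0.65 at 206 deaths and 0.68 at 260 deaths.

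**5. Check by simulation.** A log-rank simulation with 110 and 257 patients (20,000 runs, medians 7.4 and 10.1 months) gives 57% to 60% power with exactly 12 months of follow-up. With all patients dead it gives 77.7% (obese better) or 79.1% (obese worse).

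**6. Other splits.** With 0.25 in place of 0.21, a factor split 50:50 has about 62% power at 206 deaths and 72% at 260. The 54% to 64% is therefore specific to 30:70.

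**The case against.** The strongest defence is that section 3.3 never says the 80% is for obese versus non-obese. The introduction also aims at efficacy in specific subpopulations, and the primary end-point is real-world efficacy. Sizing the smallest subgroup for its own survival against a historical median fits that aim, and Section 4's Kaplan-Meier estimates with confidence intervals could be set beside 7.4 months. A formal test might stand in an analysis plan that is not at hand. This much stands: the comparison behind the 80% is inferred from the inputs, the cited method and the reproduction, and the calculation has a legitimate use. It does not rescue the figure for the obesity question. Outside the sample-size text, the protocol raises obesity only as a prognostic factor, and the tests in Section 4 compare groups.

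It is also fair that 0.73 is not the protocol's obesity effect, so another value would give another power. That calls for labelling the assumption. It does not make the 80% applicable.

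Stronger readings are tempting, but the documents do not support them:

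- *The arithmetic is wrong.* It is not; 78, 110 and 367 all reproduce.
- *80% is out of reach even if every patient dies.* At HR 0.73 this is a near-miss: 79%, with 378 deaths needed against 367 patients. Freedman's formula for unequal groups gives 337 or 433 deaths depending on direction, and 367 is stated as a minimum, not a cap.
- *All the prognostic factors have 54% to 64% power.* That range holds only for a 30:70 split.
- *The 78 events cover second-line patients only.* The 110 and 367 pool both lines; only the reference is second-line.

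**Conclusion.** The point holds as a mismatch between the sample-size rationale and the planned analysis. The stated 80% fits obese patients against an external 7.4-month chemotherapy median and does not describe the obese versus non-obese comparison. For that comparison, 367 patients give about 54% to 64% power, assuming HR 0.73 (borrowed), a 30:70 split, two-sided 5% and 56% to 71% of patients dead. The upper end uses the plan's own event share. The lower end takes 12 months as the whole follow-up, although the protocol states it as a minimum. A larger cohort or longer follow-up would raise these figures.

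A reader might infer that the study will report a null obesity result as evidence of no effect. The protocol states no such rule; the risk is that the present wording invites it.

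Even as a one-sample calculation, the benchmark is imperfect: it sets a second-line median against a cohort that includes first-line platinum-unfit patients.

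**What to change.** In section 3.3:

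1. State that the 80% refers to obese patients against the external 7.4-month reference, and that this reference is second-line while the cohort pools first- and second-line patients. Do not present it as power for the prognostic comparisons.
2. For obese versus non-obese at 30:70, state that 367 patients give about 54% to 64% power at an assumed HR of 0.73, and 80% power only for an HR of about 0.65 to 0.68 or stronger. Label the HR and the event shares as assumptions.
3. Say that factors with other splits need their own figure.

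In Section 4, stratify the pembrolizumab log-rank and Cox comparisons by line of therapy, or adjust for it. Treatments are already among the data collected.

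The cost is a few sentences, one model term and a less favourable stated power. No extra patients are needed.

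### Section 3.3's 110 obese patients and 78 deaths do not follow from its own conditions: at the 12-month minimum, HR 0.73 gives about 62 expected deaths

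*Protocol*

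**What the plan says.** Protocol section 3.3 sizes the pembrolizumab cohort on its smallest planned subgroup, obese patients, taken as 30% of the population.

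- Reference values, from the cited registration study: "the median OS in the standard control arm with chemotherapy was 7.4 months, with a hazard ratio of 0.73".
- Operating characteristics: "we set a significance level of 0.05 and the power to 80% for a minimal observation time of 12 months".
- Result, presented as following from those conditions: "we estimated an enrollment of 110 obese UC patients, in order to expect to observe at least 78 events in this group". The overall target of 367 patients is derived from this.
- Section 4 adds: "Significance levels will be set at a 0.05 value and all p values will be two-sided".

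The 12-month minimum is the only follow-up figure in the calculation. No accrual window and no average or maximum follow-up is given. The paragraph names no test. It cites two references ([22] and [25]) whose titles concern life testing, one of them exponential life testing.

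**The concern.** Seventy-eight deaths among 110 patients means that 70.9% have died. With a control median of 7.4 months and a hazard ratio below 1, an exponential curve does not reach that proportion by month 12 under either hypothesis. The number of deaths determines the power, and the 110 is what becomes the 367-patient target. If the event count does not follow from the listed conditions, a reader cannot tell what follow-up, hypothesis or sidedness the target rests on, or what power the stated minimum secures.

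**Working it through.** **Inputs.** From section 3.3: control median 7.4 months, HR 0.73, significance level 0.05, power 80%, minimum observation 12 months, 110 obese patients, 78 events, obese share 30%. From section 4: two-sided tests. Assumptions: exponential survival and a one-sample test (inferred from references [22] and [25]), and no loss to follow-up before month 12.

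**1. The plan's own figures.**
- Overall target: 110/0.30 = 366.7, so 367. Reproduced.
- Required events, one-sample exponential, two-sided 0.05, log approximation: ((1.960 + 0.842)/ln 0.73)² = 79.2.
- Exact version: the smallest r with χ²(0.975; 2r)/χ²(0.20; 2r) ≤ 1/0.73 is r = 77. The stated 78 lies between the two, so it is sound as a two-sided one-sample requirement.
- Two-group log-rank formulas give 250 to 378 events, depending on formula, sidedness and allocation. They are not the basis.

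**2. Expected deaths at exactly 12 months.** Deaths = 110 × (1 − 0.5^(12/median)).

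| Hypothesis | Median (months) | Dead by month 12 | Deaths among 110 |
|---|---|---|---|
| HR 0.73 | 7.4/0.73 = 10.14 | 56.0% | 61.6 |
| Null | 7.4 | 67.5% | 74.3 |
| Needed | – | 78/110 = 70.9% | 78 |

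The step from 78 events to 110 patients therefore fails at 12 months under both hypotheses.

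**3. Two-sided power to detect HR 0.73.** Log approximation: Φ(√d × 0.3147 − 1.960), where 0.3147 = |ln 0.73|. The exact chi-square result is alongside.

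| Deaths d | Log approximation | Exact |
|---|---|---|
| 62 | 70% | 72% |
| 74 | 77% | 79% |
| 78 | 79% | 81% |

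The row for 62 is the relevant one at the 12-month floor, because power is evaluated under HR 0.73. The row for 74 applies only if events were counted under the null.

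**4. Follow-up that would give 78 deaths from 110.**
- Same follow-up for everyone: t = median × log₂(1/(1 − 78/110)) = 18.1 months under HR 0.73, or 13.2 months under the null.
- Uniform follow-up from 12 to 12 + A months, with λ = ln 2/median: deaths = 110 × {1 − [e^(−12λ) − e^(−(12+A)λ)]/(λA)}. Under HR 0.73, A = 13 gives 77.9 and A = 24 gives 86.2. Under the null, A = 2 gives 77.4 and A = 3 gives 78.8.

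**5. Patients needed for 78 deaths if follow-up were exactly 12 months.** Under HR 0.73: 78/0.5598 = 139.3, so 140 obese patients (140/0.30 = 467 overall). Under the null: 78/0.6750 = 115.6, so 116 (116/0.30 = 387 overall).

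**6. One-sided check.** At one-sided 0.05 the requirement is 62.4 events (log approximation) or 61 (exact). At 12 months under HR 0.73, 62 events need 62/0.5598 = 110.8 patients. This nearly matches the 110, but contradicts both the stated 78 and the two-sided rule.

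**The case against.** The strongest reply is that 12 months is a minimum. In a retrospective cohort many patients will have been followed for longer, so 62 is what 110 patients would give only if nobody were observed past month 12. This stands. A reader might infer that the study will not have its 80% power, and the document does not support that. Uniform follow-up from 12 to about 25 months, for instance, gives 78 deaths under HR 0.73. What remains is that the protocol states no such follow-up, yet presents 78 from 110 as the consequence of the conditions it lists.

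A second reply is that the test is never named in section 3.3 and that sidedness comes from section 4. This is also fair: the one-sample exponential basis is an inference, supported by the references and by the 78 being reproducible. The one-sided match to 110 raises the possibility that 78 and 110 came from different assumptions. That cannot be established from the text, but it is a reason to state the basis.

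Two other readings go too far. One is that 78 deaths require an 18-month eligibility rule in section 3.1. The 18.1 months is a common fixed follow-up, not a necessary minimum, and such a rule would exclude patients needlessly. The other is that the 12-month minimum goes unenforced because section 3.1 has no treatment-start window. Section 3.3 itself sets the minimum, section 4 excludes patients with inadequate follow-up data, and an operational cut-off may sit in a statistical analysis plan that is not shown.

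**Conclusion.** The point holds as an internal inconsistency in section 3.3. At the stated minimum, 110 obese patients give about 62 expected deaths under HR 0.73, or about 74 under the null, so the promised lower bound of 78 fails either way. Under HR 0.73 the shortfall is about 16 deaths (78 − 62), roughly 20% of the stated count, and two-sided power at that floor is about 70–72%. The 78-event requirement is sound; the conversion to 110 patients is not supported by the conditions given. The result rests on exponential survival, a one-sample test, two-sided 0.05 and no loss before month 12. It shows a loss of power only at the 12-month floor and says nothing about the power that the actual follow-up will give. The passage should be corrected because it sets the 367-patient target.

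**What to change.** Amend section 3.3 in one of two ways.

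- **Restate at the floor:** *At the 12-month minimum, 110 obese patients give at least about 62 expected deaths and about 70% two-sided power for HR 0.73.*
- **Keep 78 from 110:** state the follow-up distribution that produces it, the hypothesis under which events are counted and the sidedness. Under HR 0.73, about 18 months for every patient or a uniform spread from 12 to about 25 months would do. These are illustrations, and the figure used should reflect the treatment-start dates in the database.

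In either case, define the minimum as time from treatment start to data cut-off, not as observed follow-up. If it were read as observed follow-up, patients who died before month 12 would be removed and OS would be biased upward.

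The cost is a text correction. No extra enrolment and no 18-month eligibility rule are needed. The downside is that the power stated at the 12-month minimum becomes less favourable.

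### The enfortumab vedotin sample size names no null rate, writes power as β, and gives 311 and 361, which do not follow from the stated inputs

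*Protocol*

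**What the plan says.** The second paragraph of Protocol Section 3.3 takes 12-month survival from the enfortumab vedotin approval trial. For the drug itself it reports "51.5% (95% CI, 44.6 to 58.0) in the enfortumab vedotin group". The comparator rate, under chemotherapy, is put at 39.2%, and the gap between the arms at 12.3 points. The paragraph goes on to the study's own hypothesis, that "OS would reach at least 60% after 12 months from the start of therapy".

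The enrolment figure comes first: "Study plan will include at least 361 patients with an estimated drop out of" (the range named is 10–15%). The evaluable number is then given as "minimum of 311 evaluable patients should be enrolled with an α of 0.05 and a β of 0.80".

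Section 4 adds the general rule "Significance levels will be set at a 0.05 value and all p values will be two-sided". It plans Kaplan-Meier estimates of OS with 95% confidence intervals. The pembrolizumab paragraph, just above in Section 3.3, sets power (not β) at 80%.

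**The concern.** A sample size with an α and a power needs two rates: one to reject and one to detect. Section 3.3 supplies only the second, 60%. Two published rates stand beside it, but neither is named as the null, and the quoted difference of 12.3 points is between the arms of the cited trial, not between this study's target and a benchmark.

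Three further figures do not fit. The β is given the value that belongs to power. The evaluable number does not come out of the quoted rates at the stated error levels. The enrolment figure does not cover the upper end of the stated drop-out range.

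This is the only quantified hypothesis for enfortumab vedotin, and the drug's efficacy is part of the primary endpoint (Section 2.1). Without a null, a reader cannot tell what a given 12-month OS would show or what 311 patients were meant to deliver.

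**Working it through.** **Inputs (Protocol Sections 3.3 and 4).** Alternative p1 = 0.60. Candidate nulls p0 = 0.515 (enfortumab vedotin arm) and 0.392 (chemotherapy arm). α = 0.05, two-sided, so z = 1.960. Power read as 0.80, so z = 0.842. Evaluable 311, enrolled 361, drop-out 10–15%.

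**Formula.** One-sample proportion, normal approximation:

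n = [z_α·√(p0(1−p0)) + z_β·√(p1(1−p1))]² / (p1−p0)²

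**Step 1: can 311 be reproduced from the stated inputs?**
- p0 = 0.515: (1.960 × 0.4998 + 0.842 × 0.4899)² / 0.085² = 1.937 / 0.007225 = 268.1, so **269**. The exact binomial test first reaches 80% power at **274**; because exact power moves in a sawtooth, it stays at or above 80% only from 285.
- p0 = 0.392: (1.960 × 0.4882 + 0.842 × 0.4899)² / 0.208² = 1.875 / 0.04326 = 43.3, so **44**.

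Neither is 311.

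**Step 2: β taken literally.** β = 0.80 means 20% power, so z_β = −0.842. With p0 = 0.515, n = (0.9795 − 0.4123)² / 0.007225 = 44.5, so 45. The literal reading cannot be the source of 311.

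**Step 3: what does give 311?** Each of these changes an input:

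| Null | Test | Power | n |
|---|---|---|---|
| 51.5% | two-sided | 85% | 307 (exact: first reached at 311) |
| 52% | two-sided | 80% | 303 |
| 52.1% | two-sided | 80% | 311 |
| 53% | one-sided | 80% | 311 |

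Two of these settings also return 361 at a higher power: the exact two-sided test of 51.5% first reaches 90% there, and the one-sided 53% setting needs 361 for 85%. Several routes lead to the same numbers, and the protocol states none of them.

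**Step 4: power with 311 and a true rate of 60%, two-sided 0.05.**
- Against 51.5%: Φ[(0.085·√311 − 1.960 × 0.4998) / 0.4899] = Φ(1.06) = **85.6%** (exact 85.4%).
- Against 39.2%: above 99.9%.
- Against 58.0%, the upper confidence limit of the quoted enfortumab vedotin rate: about 10%.

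The spread shows how far the power depends on the null that is not named.

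**Step 5: drop-out.**
- 361 × 0.90 = 324.9, above 311.
- 361 × 0.85 = 306.9, so 306 whole patients, **5 below the minimum**.
- Break-even: 1 − 311/361 = 13.85%. A loss of 13.8% leaves 311.2; 13.9% leaves 310.8.
- Enrolment needed to keep 311: 311/0.90 = 345.6, so 346; 311/0.85 = 365.9, so **366**.
- Power with 306 against 51.5%: 85.0% (exact 82.8%).

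**The case against.** The strongest reply is that the intent is clear and the errors do no harm. The 60% follows directly on the published 51.5% for the same drug, so the ordinary reading is 51.5% as benchmark and 60% as target. On that reading 311 exceeds what 80% power requires. The β is a labelling slip that the paragraph above exposes. The 361 figure fits 311 at a loss of 13.8%, inside the stated range, and is worded as a floor. Section 4 already provides the Kaplan-Meier estimate with a 95% interval, which is all the test needs, and the exact decision rule may stand in a statistical analysis plan that is not shown. The study is retrospective and its primary endpoint is worded descriptively.

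Most of this stands, and it limits the weight of the point. It does not remove it: the null must be guessed, the β is wrong as printed, 311 is not the 80% figure for either quoted rate, and 361 fails at the drop-out the protocol itself allows.

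Three stronger readings are tempting but unsupported:
- *The cohort is underpowered, or no test has the claimed power.* Against 51.5% the power is about 85%, above the claim.
- *311 betrays a hidden one-sided test against 53%, in breach of the two-sided rule.* The two-sided exact test of 51.5% against 60% also gives 311, at 85% power, so the source cannot be inferred.
- *Success requires an estimate of at least 60%, or a lower limit above 60%.* The protocol states neither rule, so power figures for them describe a different study. Nor does it say that the rule will be chosen after the data are seen.

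**Conclusion.** The paragraph is wrong as written and should be corrected, but the correction concerns definition and reporting, not lost power.

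- The null rate is missing, so the stated power attaches to no defined comparison.
- β = 0.80 should be power 0.80 (β 0.20).
- 311 overshoots the 80% size for 60% against 51.5% by 42 patients (311 − 269), or by 37 against the exact figure (311 − 274); its power there is about 85%.
- 361 falls 5 short of the minimum at 15% drop-out, is sufficient up to 13.8%, and even at 306 keeps 83–85% power against 51.5%.

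The power figures assume that 51.5% is the intended null, that the true rate is 60%, and that 12-month status is known for every evaluable patient. Censoring before 12 months would lower the power somewhat; the protocol gives no figure from which to quantify that.

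**What to change.** Rewrite the enfortumab vedotin paragraph of Section 3.3:

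1. State H0: 12-month OS = 51.5% against H1: 60%, two-sided α 0.05, judged by whether the lower limit of the 95% confidence interval for the Kaplan-Meier 12-month OS exceeds 51.5%. If the sponsor meant another null, name it and recompute.
2. Replace the β of 0.80 with power 0.80 (β 0.20).
3. Either keep 311 and state that it gives about 85% power, or give about 269 (exact 274) as the 80% figure.
4. Either keep 361 and state that it tolerates a loss of up to 13.8%, or raise it to 366 to cover 15%.

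The cost is one paragraph and one stated decision rule. No extra patients are needed if the tolerated loss is restated; 5 more (366 − 361) if the 15% bound is kept with 311.
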